- “The Australian Clinical Practice Guidelines for the Management of Overweight and Obesity in Adults” (NHMRC, 2013) provide an evidence-based, stepped approach to obesity management. The first level of management is lifestyle intervention, comprising exercise, nutrition and psychological intervention. The second level of management is medication management. The third level of management is surgery. The guidelines consider that higher levels of management are indicated when lower levels of management have been insufficient to achieve desired clinical outcomes. This is the management approach the hospital research team will adopt in their patient management strategies.
- However, the control group in this study will receive ‘usual care’. The research team is aware this means patients in the intervention or control groups may receive lifestyle, medication and / or surgical management through alternative clinical pathways (e.g. through primary care, private hospital or other sources of clinical support). This is usual in obesity clinical trials with a ‘usual care’ control arm (see the Australian Clinical Guidelines discussion on this). Consistent with other obesity studies, we will account for any differences post-hoc in our data analysis.

AMOS Research Project Participant Flow Chart

Study Duration/Timelines:

Stage 1: Recruitment of participants to study and informed consent (0 – 3 months)

Stage 2: Data collection, referral to therapies (3 – 12 months)

Stage 3: Ongoing recruitment and informed consent (6 – 9 month)

Stage 4: Initial data analysis (15 months)

Stage 5: Data Analysis and Interpretation (24-26 month)

Stage 6: Presentation and publication (15 and 26 month)

Study Population

Participants

Inclusion Criteria

- Person with BMI >30 with waist circumference \geq 88cms in women and \geq 102cms in men
- Those aged < 75 years of age
- Patient has diabetes mellitus
- Already in the care of the North West diabetes service
- Able to provide informed consent
- Not pregnant or breastfeeding

Exclusion Criteria

- Person with diabetes with a BMI > 30 with waist circumference < 88cms in women and <102cms in men
- Person with diabetes with a BMI \leq 30
- Those aged \geq 75 years of age
- Any pregnant or breastfeeding person with diabetes
- Any person with diabetes < 18 years of age
- Any person with a cognitive impairment, an intellectual disability or uncontrolled psychotic illness

Lay Description of Participation

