 - HbA1c
 - Absolute cardiovascular risk
 - Psychometric measures (PHQ-9, depression and SF-36 Quality of Life)
 - Decline in Edmonton Obesity status (Padwal, 2011)
- Rationale - the power is in general a function of the possible distributions under the alternative hypothesis. As the power increases, the chances of a Type II error occurring decrease. We conducted power calculations to calculate the minimum sample size required using a target variance for an estimate to be derived from the sample eventually obtained.
- We assumed a Cohens d of 0.5 and a power of 0.95 based on estimates in the peer-reviewed literature.
- We assumed significance criteria of 0.05, the probability of the data implying an effect at least as large as the observed effect when the null hypothesis is true must be less than 0.05, for the null hypothesis of no effect to be rejected.
- Further, this assumed:
 - A follow-up period of at least 6 months for each participant.
 - Not all participants will be cared for simultaneously – there will be multiple intakes e.g. as people exit the program enrol new participants and controls.

Analysis TSRAC Q12

- Data will be exported from DiaBASE (Clinical software program) and entered into Excel (Microsoft) for data cleaning, then imported into Stata 12 and SPSS for analysis.
- Analysis will be performed using SPSS and Stata.
- Descriptive statistics will first be calculated to investigate the proportions of categorical variables and the distribution of continuous variables.
- Pearson's chi-square test or Fisher's exact tests will be utilized for investigation of associations between categorical variables, while independent t-tests will be used to investigate differences in continuous data between the control and intervention groups.
- For dichotomous outcomes logistic regression will be performed.
- For continuous outcome data analysis of covariance will be performed to test the effects of predictor variables.
- Adjusted relative risks (aRR) of metabolic and psychometric outcomes will be calculated for the control vs. intervention groups (with 95% confidence intervals) using a Poisson regression model with robust error variance.
- The regression models will include adjustment for age, pre-existing diabetes, socio-economic status and Asian or indigenous ethnicity.

Please provide additional justification on for the effect size with references.

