- Co-Principal Investigator/Project Manager will meet with Case Manager to identify any problems with follow-up and/or implementation of therapy plans.
- Study co-ordinator/Project manager will meet with recruiting staff to ensure training has been adequate and well supported for screening, recruiting and consenting of participants.

Data and Safety Monitoring

The likelihood of a serious adverse event occurring in this study is low and consequently there are no stopping rules. Given the short timeframe of this study 2.5 years it is unlikely that the issue of overwhelming benefit or futility will arise. Thus a Data and Safety Monitoring Board will not be established. Reports on Risk Assessment and Management will be provided to the Safety and Quality Committee of the THO on a 6 monthly basis.

Resources

Others Personnel Relevant to the Research Project

- [name]: Director Populations Health Operations- involved in the supporting of analysis of data to provide input in policy direction
- [name] (RN BN Diabetes Educator) /[name] (RN BN CDE): Research Assistant/Case Manager - ensuring participants receive care and therapies that have been planned, data collection and entry, and reviewing of data for completeness
- [name]: Manager of physiotherapy, provision of staffing for the study. May access the information to review factors that may relate to the role of the physiotherapist
- Surgeon TBA: Will provide assessment and review of patients deemed suitable for bariatric surgical procedures
- [name]: Manager of Pathology – involved in the provision of advice in pathology screening, will not access data
- [name]: Manager of the Diabetes Centre – involved in support clinics with staffing, will not access data – but may use final findings to change service delivery

Training

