- Assessment (utilising referral to appropriate health professionals if required) should also include other physical comorbidities associated with excess weight, including:
 - symptoms of sleep apnoea (snoring, frequent waking, daytime hypersomnolence)
 - signs of arthritis, especially in the hip and knee joints
 - symptoms of gastro-oesophageal reflux disease (GORD)
 - assessment of right-heart function for evidence of pulmonary hypertension or right-heart failure
- Ensure informed consent of participants and ethics approval sought and documented
- Monitor the project's budget as presented by the funded proposal
- Managing change, alterations and timelines
- Co-ordinate and/or provide relevant training (eg data collection)
- The research will be conducted under the supervision of a steering committee comprised of members of the clinical team caring for the patients, experts in population health and with academic oversight.
- Communications to the project team on project
- Report on progress of project to THO-North West Quality and Safety Committee at each 6 month interval and at completion of project.
- Present and/or contribute to presentations of the project to relevant workshops or seminars organised by vTAHSP.
- Perform audits of data for accuracy and completion
- Analysis and interpretation of data
- Involved in publications and presentation of data/results at relevant venues. Share project evaluation with the Tasmanian Health Council and state-wide Diabetes Leaders Group on conclusion of the project to promote replication and sustainability

Lead Academic – Research Fellow

- Involved in providing advice and instruction of evaluation of the project and planning data collection.
- Involved in the planning and development of operational business processes for the clinic and data collection
- Supports completion and submission of ethics application for research project within project timelines
- Communications to the project team on the project and data collection
- Supports in drafting the report on progress of project to THO-North West Quality and Safety Committee at each 6 month interval and at completion of project (04/15, 10/15, 4/16, 10/16).

- Present and/or contribute to presentations of the project to relevant workshops or seminars organised by vTAHSP.
- Analysis and interpretation of data (10/2016, 4/2017, 10/2017, 6/2018) to evaluate the model and for the purpose of reports.

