Physiotherapy

- Involved in planning and development of business processes for access criteria, consent, therapies and data collection
 - Space for assessment and individual or group management
 - Evidence based Assessment protocol including Pain Assessment tool
 - Formulation of Template for Exercise Programme with progression/review capacity
 - Care/Treatment Plan – incorporate data as available for team review
 - Outline group strength/resistance training programme(s) – evidence based
 - Determine validated Outcome Measures – eg. 6 minute walk test; stair climbing test
- Involved in relevant agreed data collection for purposes of reporting and investigating including:
 - Completion of McCaffery Pain assessment scale
 - Completion of a full physical functioning and balance assessment (6 minute walk test (6MWT), Timed Up and Go (TUG), 30-second Chair Stand test (30s-CST)
 - Investigate iPM Clinics structure
 - Utilise ABC – Activity Barcoding Data Collection
 - Providing any relevant information to support progression of 3 monthly progress report as required by vTAHSP.
- Involved in providing Education and Support to the clinic:
 - Collate and share data with the Team for education/research/clinical or funding purposes
 - Utilise data collected to develop presentations for relevant community and professional groups
 - Assist in presenting and/or contribute to presentations of the project to relevant workshops or seminars organised by vTAHSP.
- Involved in the Evaluation and Research activities of the clinic/project:
 - Background searches for evidence on predictors of weight loss associated with physical activity in the obese/diabetic person
 - Support for ongoing trials/research via data sharing , clinical and professional involvement
 - Involved in supporting analysis and interpretation of data

Population Health

- Involved in planning and development of operational business processes for inclusion of self-management programs
- Supports project reporting requirements with advice as relevant (04/15, 10/15, 4/16, 10/16).
- Analysis and interpretation of data (12/2016, 6/2017, 6/2018) to evaluate the model and for the purpose of reports.
- Review of data collection by Population Health - although challenging to draw conclusively from a trial that will last for 12 months and inevitably have a relatively small population, it will be able to “point” to further actions and strategies (0, 12, 24 months).

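### The study timeline analyses at months 24–26 and publishes at month 26, but the last 24-month primary outcome visit falls at month 33, and no analysis is named as confirmatory

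*Protocol*

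**What the plan says.** Study Duration/Timelines gives two recruitment windows: "Stage 1: Recruitment of participants to study and informed consent (0 – 3 months" and "Stage 3: Ongoing recruitment and informed consent (6 – 9 month". It places an initial data analysis at month 15, then "Stage 5: Data Analysis and Interpretation (24-26 month", then "Stage 6: Presentation and publication (15 and 26 month". No later analysis appears in that section.

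The Outcomes section sets HbA1c at 6, 12, 18 and 24 months post baseline and body weight at 12 and 24 months. Both are also measured 6 and 12 months post intervention. The intervention itself lasts up to 24 months.

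Other sections describe the study's length and analyses differently:

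- Data and Safety Monitoring: "Given the short timeframe of this study 2.5 years".
- Project Management, Lead Academic: "Analysis and interpretation of data (10/2016, 4/2017, 10/2017, 6/2018) to evaluate the model and for the purpose of reports".
- Project Management, Population Health: analyses at 12/2016, 6/2017 and 6/2018, and also "a trial that will last for 12 months and inevitably have a relatively small population".
- Sample Size: "A follow-up period of at least 6 months for each participant", with several intakes and new enrolment as people leave the programme.

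**The concern.** The timeline's analysis and publication dates cannot be met with complete 24-month data on its own recruitment windows. A team that follows the section as written would analyse and publish a 24-month primary comparison drawn only from the earliest recruits. It would have much less than the planned power and no post-intervention results for anyone who completed the full programme.

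Later analysis dates do exist, but they sit in role descriptions. Nothing links them to the primary comparison, so a reader cannot tell which analysis the trial's conclusion will rest on.

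**Working it through.** **Inputs.** Recruitment windows, analysis at months 24–26 and publication at month 26 are from Study Duration/Timelines. The 24-month outcome is from Outcomes. The total of 212 (106 per arm), d = 0.5, power 0.95 and significance level 0.05 are from Sample Size. The study length of 2.5 years (30 months) is from Data and Safety Monitoring.

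**The plan's own sample size.** Taking the test as two-sided (not stated), n per arm = 2(1.96 + 1.645)² / 0.5² ≈ 104. The t-test version gives 105. The stated 106 gives power 0.952. The figure reproduces.

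**Dates.**
- Last 24-month visit: 9 + 24 = month 33. This is 7 months after month 26 and 3 months after month 30.
- First post-intervention value after a full 24-month programme: 24 + 6 = month 30 for someone recruited at month 0; the 12-month one is at month 36. Both are after month 26.

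**Share with a 24-month value at calendar month T.** This is the share enrolled by month T − 24. At T = 26 it is the share enrolled by month 2. The Protocol gives no accrual rate or split, so I assume uniform accrual within each window, no dropout and exact visit timing. If a fraction w enters in months 0–3, the share is w × 2/3. With continuous accrual over months 0–9 it is 2/9. Power is for a two-sided t-test at d = 0.5.

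| Assumed accrual | With 24-month value at month 26 | Without | Per arm with value | Power |
|---|---|---|---|---|
| All in months 0–3 | 141 (67%) | 71 (33%) | about 70 | 0.84 |
| 75% / 25% | 106 (50%) | 106 (50%) | 53 | 0.72 |
| 50% / 50% | 71 (33%) | 141 (67%) | about 35 | 0.54 |
| Continuous, months 0–9 | 47 (22%) | 165 (78%) | about 23 | 0.39 |
| 25% / 75% | 35 (17%) | 177 (83%) | about 17 | 0.30 |

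At month 24, the start of the analysis stage, almost nobody has a 24-month value in any scenario. At month 30, even accrual gives 106 participants with a value (53 per arm) and power 0.72. At month 33 all 212 have reached the visit. Enrolment beyond month 9, which the Sample Size text could allow, would move month 33 later.

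**The later dates.** The list of potential participants is dated 10/9/2014 (Randomisation), and progress reports start at 04/15 (Project Management). If month 0 lies between late 2014 and mid 2015, which is an assumption, 6/2018 is about month 36 to 45. That is after month 33.

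**The case against.** The strongest reply is that the month 24–26 stage is never called final. Two role descriptions list an analysis at 6/2018, which would probably hold every 24-month value. On that reading the trial loses no power and the timeline is simply out of date. This largely stands. A reader might infer that about two thirds of participants will lack the outcome at the final analysis; the documents do not support that. The two-thirds figure needs even accrual, and the month-26 analysis may not be the final one. What remains is that the only timeline section ends at month 26 with a publication, and nothing overrides it.

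The 24-month value is also one of several primary time points. Every participant reaches 12 months by month 21 (9 + 12), so a month-26 analysis could include 12-month data on both primary outcomes. That is true, and it limits the power loss to the 24-month comparison. It does not justify moving the primary time point, which would change the trial's question to cure a scheduling conflict.

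Three further inferences go too far:

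- *The 6-month follow-up assumption contradicts 24 months.* It is stated as a minimum, so it does not. The 12-month trial length under Population Health does conflict, although it is a passing remark and the same bullet ends with reviews at 0, 12 and 24 months.
- *Repeated looks inflate the type I error on top of the power loss.* The power loss requires the month-26 analysis to be the last; the longer series of looks requires the schedule to 6/2018. Both cannot be charged together, and the Protocol states no rule for testing at each date.
- *Publication at month 15 will bias the remaining follow-up.* The timeline does not say that between-arm outcomes will be released then. With visibly separate clinics for the two arms, this is a conditional risk worth closing off.

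**Conclusion.** The contradiction is established from the Protocol's own dates and needs no accrual assumption: month 33 is later than the month 24–26 analysis, the month-26 publication and the 2.5-year study length.

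The size is conditional on the month 24–26 analysis being confirmatory. In that case 33% to 83% of participants lack a 24-month value even at the latest cut-off, and power at d = 0.5 is about 0.84 to 0.30. Even the most favourable split, which ignores the second recruitment window, leaves a third without the value. Dropout would make these figures worse.

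If the 6/2018 analysis is the confirmatory one, the loss probably disappears, given the assumed start date. The Protocol does not say which applies, and that omission is the point to correct.

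**What to change.** - Reconcile Outcomes, Study Duration/Timelines, Data and Safety Monitoring, and the Lead Academic and Population Health entries under Project Management. This includes the 2.5-year and 12-month study lengths.
- State that the confirmatory 24-month analysis and its publication follow the last participant's 24-month visit: month 33 on the stated windows, or later if enrolment continues. The listed 6/2018 date should cover this once the start date is confirmed.
- State when the post-intervention values will be analysed.
- Label the month 15 and month 24–26 analyses as interim or descriptive, and release no between-arm primary outcome results while follow-up continues.

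The change is to wording and needs no extra participants. The price is a main publication about 7 months later than month 26.

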Finally, the systematic review of the literature performed for the development of the national guidelines reveals a lack of evidence for chronic disease models of obesity care rather than models of care that focus on weight loss as the main goal of care (NHMRC, 2013). Chronic disease models of care are of particular relevance to patients with obesity and type 2 diabetes as the likelihood of sustained weight loss in this patient group, even with surgical intervention, has been shown to be low (NHMRC 2013; National Institute for Health and Care Excellence, 2013). It is therefore essential that the secondary complications of obesity (sleep apnoea, hypercholesterolaemia, hypertension, malignancy, infertility, non-alcoholic steatohepatitis, osteoarthritis) (ADIPS 2013; National Cancer Institute 2013; NHMRC, 2013) are identified early and managed effectively in these patients as sustained weight loss is unlikely in spite of weight reduction therapies (NHMRC 2013; National Institute for Health and Care Excellence, 2013).

Study Goals and Objectives

AIM

The aim of this study is to assess the feasibility, acceptability and effectiveness of a rural, multidisciplinary team-based approach to care for adult patients with diabetes mellitus and obesity.

OBJECTIVES OF THIS PROJECT

- To determine if a multidisciplinary multi-intervention clinic for obesity tailored to the individual can reduce absolute cardiovascular and morbidity risk
- To evaluate management and treatment factors as potential predictors of outcome
- To determine whether an interdisciplinary multi-intervention obesity clinic for people with diabetes improves metabolic profile
- To provide process and impact outcomes to substantiate and drive clinical and policy change supportive of a multidisciplinary systematic approach for patients living with obesity

OUTCOMES

Primary Outcome:	change in HbA1c (measured as a continuous variable) in the intervention group compared with the control group
Timepoint:	at 6, 12, 18 and 24 months post baseline; also 6 and 12 months post intervention
Primary Outcome:	change in body weight (measured as a continuous variable) in the intervention group compared with the control group
Timepoint:	at 12 and 24 months post baseline; also 6 and 12 months post intervention
Secondary Outcome:	a decline in Edmonton Obesity status
Timepoint:	at 12 and 24 months post baseline, and 12 months post intervention

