Secondary Outcome:	change in absolute cardiovascular risk
Timepoint:	at 12 and 24 months post baseline, and 12 months post intervention
Secondary Outcome:	proportion of participants achieving individualised HbA1c targets according to the Australian Diabetes Society guidelines
Timepoint:	at 12 and 24 months post baseline; also 12 months post intervention
Secondary Outcome:	impact on psychometric scores as assessed using the Assessment of Quality of Life (SF-36), Patient Health Questionnaire (PHQ-9) [Depression] and Generalised Anxiety Disorder Assessment (GAD-7) [Anxiety], Assessment of Quality of Life (AQoL), Work Productivity and Activity Impairment (WPAI)
Timepoint:	at 6, 12, 18 and 24 months post baseline; also 6 and 12 months post intervention

Outcome measures and collection time points							
Measure	Base line	6 mth	12 mth	18 mth	24 mth	6 mth POST	12mth POST
Demographic and clinical measures:							
Demographic data, duration of diabetes	X						

 Demographic data, duration of diabetes at baseline only – to ensure similar characteristics of both the intervention and control groups. 							
Biometric measures; weight, BMI, girth, BP	X	X	X	X	X	X	X

 To review changes in metabolic parameters Time points to allow for intensification of treatment as deemed required Based on evidenced based guidelines/ peer-reviewed literature for timely treatment 							
Co-morbidities, medications	X		X		X		X

 To review changes (improvement/deterioration) in other co-morbidities as a result of treatment for obesity Review interval increased as changes in medication and disease profiles require review time, further based on timelines for review and assessment in peer-reviewed literature. 							
Edmonton obesity staging	X		X		X		X

 The Edmonton obesity staging system independently predicted increased mortality even after adjustment for contemporary methods of classifying adiposity (Padwal et al., 2011). The Edmonton obesity staging system may offer improved clinical utility in assessing obesity-related risk and prioritizing treatment. The project is targeting gradual weight loss that is linked to sustained weight loss – thus timing for assessment are linked to overall weight loss and potential co-morbidity reduction as estimated in peer reviewed literature 							
Sleepiness Scale	X		X		X		X

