- Participants may directly benefit from participation in the study as a result of improvements in metabolic markers
- The early identification and management of secondary complications of obesity.
- A reduction in absolute cardiovascular risk.
- An improvement in glycated haemoglobin - or diabetes control.
- A potential reduction in body weight.

Risk of Harm

Low Risk – It is possible that participants may find some of the physical activities challenging and/or psychological sessions distressing. However, the study protocol directs those with higher levels of stress for therapies to reduce anxieties and distress. These are measured throughout the study at 6 month intervals.

Some participants will be referred for bariatric surgery. This surgery is associated with complications and adverse events. These are not a result of the study per se as the surgery is not experimental and is an established clinical treatment recommended in current national guidelines.

Other Risks

There are no foreseeable risks to the research team or the organisation.

Commercial Benefits of the Research for Investigators and Sponsors

There is no anticipated commercial benefit arising from the research for the investigators and/or sponsor

Risk of Harm as a Result of Dissemination

All data will be aggregated and de-identified and thus there is no foreseeable risk of harm when results are disseminated.

Mechanisms to monitor the Project

- The research will be conducted under the supervision of a steering committee comprised of members of the clinical team caring for the patients, experts in population health and with academic oversight.
- The clinic itself will operate under the supervision of the usual clinical governance of the North West Tasmanian Health Organisation (THO). All providers are staff members of THO North West, are credentialed to provide the clinical services outlined in the model and are subject to the safety and quality monitoring and reporting requirements of the North-West Regional Hospital, an accredited Australian public hospital.
- Regular monthly to 2 monthly meetings of the study investigators to monitor the conduct and progress of the study, and to manage change, problems and timelines.
- Meetings will review; participant recruitment rate, follow-up of participants according to key outcome timelines, reasons for attrition, data collection/entry and related issues, need for early termination of study.

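### HbA1c and weight are measured repeatedly but compared by t-tests that ignore intermediate visits, so drop-out that differs by arm could bias the 24-month contrasts

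*Protocol*

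**What the plan says.** Under Outcomes, the protocol names two continuous primary outcomes, each a change compared between arms. HbA1c is assessed "at 6, 12, 18 and 24 months post baseline; also 6 and 12 months post intervention". The second is "change in body weight (measured as a continuous variable) in the intervention group compared with the control group", at 12 and 24 months and at 6 and 12 months post intervention. In the table of outcome measures and collection time points, the row "Biometric measures; weight, BMI, girth, BP" is marked at all seven time points, as is HbA1c. Weight is therefore also recorded at 6 and 18 months.

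The Analysis subsection (TSRAC Q12) fixes the method: "independent t-tests will be used to investigate differences in continuous data between the control and intervention groups". It adds: "For continuous outcome data analysis of covariance will be performed to test the effects of predictor variables". The covariates follow: "The regression models will include adjustment for age, pre-existing diabetes, socio-economic status and Asian or indigenous ethnicity". No baseline or earlier-visit HbA1c or weight is listed, and no repeated-measures method is named.

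On missing values, Data Management says only that gaps will be followed up by project staff. Mechanisms to monitor the Project puts "reasons for attrition" on the agenda of investigator meetings.

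**The concern.** A t-test at 24 months needs a 24-month value. Because the outcome is a change, baseline enters by subtraction, but the 6-, 12- and 18-month values do not enter at all. A patient seen at 6, 12 and 18 months who misses month 24 adds nothing to the 24-month result. The ANCOVA as described does not help: it also needs that visit's value, and none of its covariates carries the patient's earlier course.

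This matters if patients who leave were doing better or worse than those who stay, and if that pattern differs by arm. A difference is plausible. The arms attend openly different clinics, and withdrawal means a change of care for an AMOS patient but not for a control. The sample size also assumes only at least six months of follow-up, so a 24-month value is not assured for everyone. What is at stake is the later contrasts on both primary outcomes, when the data that could reduce the problem are already scheduled for collection.

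**Working it through.** **The plan's own figure.** The Sample Size subsection says: "We assumed a Cohens d of 0.5 and a power of 0.95 based on estimates in the peer-reviewed literature". With two-sided alpha 0.05 (sidedness is not stated, but one-sided gives only 87 per arm), n per arm = 2(z₀.₉₇₅ + z₀.₉₅)²/d² = 2(1.960 + 1.645)²/0.5² ≈ 104. The exact t-test version gives 104.93, so 105. The planned 106 per arm has power 0.954 (normal) or 0.952 (t). The stated 212 is thus reproduced, but for a two-sample t-test on complete data. If 10%, 20% or 30% lack the visit (95, 84 or 74 per arm left), t-test power is 0.93, 0.90 or 0.86.

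**Bias under drop-out.** From the protocol: 106 per arm, visits at 6, 12, 18 and 24 months, true difference 0 or −0.50 SD. Assumed, because the documents do not give them:
- change scores with SD 1 and correlation 0.6 or 0.8 between adjacent visits, decaying with distance;
- drop-out that is permanent, with probability 1/(1 + exp(2.3 − b·y)) after each of the first three follow-up visits, where y is the last observed change and higher is worse.

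With b = 0 the loss per interval is 1/(1 + e^2.3) = 0.091, so the loss by month 24 is 1 − 0.909³ = 0.249. Across scenarios it is 21-29%. There were 1,500 simulated trials per scenario. The all-visit estimate is a multivariate-normal likelihood fit in each arm.

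| Mechanism (b control, b AMOS) | Correlation | t-test, truth 0 | t-test, truth −0.50 | All visits, truth 0 / −0.50 | t-test type I error |
|---|---|---|---|---|---|
| Unrelated to outcome (0, 0) | 0.6 | 0.005 | −0.495 | 0.004 / −0.496 | 4.9% |
| | 0.8 | 0.006 | −0.494 | 0.004 / −0.496 | 5.1% |
| Same in both arms (0.8, 0.8) | 0.6 | 0.006 | −0.469 | 0.005 / −0.494 | 3.9% |
| | 0.8 | 0.006 | −0.453 | 0.005 / −0.495 | 4.3% |
| Poor responders leave AMOS only (0, 0.8) | 0.6 | −0.089 | −0.564 | 0.004 / −0.495 | 8.5% |
| | 0.8 | −0.145 | −0.605 | 0.004 / −0.496 | 15.3% |
| Opposite in the two arms (−0.5, 0.8) | 0.6 | −0.144 | −0.619 | 0.004 / −0.496 | 14.7% |
| | 0.8 | −0.238 | −0.697 | 0.003 / −0.496 | 31.7% |

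The same mechanism in both arms attenuates the effect by 0.50 − 0.469 = 0.03 to 0.50 − 0.453 = 0.05 SD. Selection in AMOS only exaggerates it by 0.564 − 0.50 = 0.06 to 0.605 − 0.50 = 0.11 SD when the effect is real, and by 0.09 to 0.15 SD when there is none.

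**Sensitivity to the slope.** With no true effect, 20% AMOS loss and selection in AMOS only, slopes of 0.5-1 per SD gave a bias of 0.04-0.08 SD (constant correlation 0.6) or 0.06-0.12 SD (decaying correlation 0.8). A slope of 2 gave 0.12 or 0.20 SD. Values near 0.30 SD appeared only with strong selection and loss around 30%.

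**Scale.** A bias of 0.05-0.2 SD is 10-40% of the design effect of 0.5 (0.05/0.5 and 0.2/0.5). The meta-analysis of lifestyle interventions cited in the effect-size justification gives longer-term effects of 0.34 for HbA1c and 0.06 for weight.

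**The case against.** The strongest reply is that the t-test sentence follows the descriptive statistics, sits beside chi-square tests, and names neither HbA1c, weight nor a primary analysis. The protocol does not say that patients missing a visit are excluded, and rules for missing data are commonly left to the analysis plan. This stands in part. The exclusion is a consequence of how a t-test works and is not a stated rule. But the t-test is the between-arm method the protocol fixes for continuous data, and the ANCOVA offered beside it does not use the earlier values.

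A reader might infer that the plan will overstate the AMOS effect. The documents do not support that. They give no drop-out rate, correlation or mechanism, and the mention of attrition is a meeting-agenda item, not a forecast. With equal mechanisms the type I error holds, and a real effect is slightly understated. Nor does the near-zero bias of the all-visit analysis show that it removes bias in general: loss was simulated to depend on observed values only, so that result is built in.

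The loss may also be smaller than feared. Participants remain patients of the service, and those who withdraw return to the usual clinic, where BMI and HbA1c are measured at pre-assessment. Data completeness is reviewed quarterly, and the case manager checks that data are up to date at collection points. Leaving AMOS need not mean losing the outcome, although the protocol does not say such values will be used.

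Finally, a reader might take the omission of 6- and 18-month weight from the primary time points for an error. It is not one: the measures table gives these visits another purpose, the review of treatment. They are simply available as information.

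**Conclusion.** The point holds in conditional form, as a cheap improvement. The protocol names a between-arm method that ignores visits it already schedules. The 24-month contrasts could be biased if drop-out depends on earlier response and differs by arm, which is plausible here but not stated. Under assumed loss of 20-30% and correlation of 0.6-0.8, the size is about 0.05-0.2 SD when poor responders leave AMOS only. It is larger only with steep selection or with the arms selecting in opposite directions. There is no bias if loss is unrelated to outcome, and an attenuation of about 0.03-0.05 SD if the mechanism is the same in both arms. All of these sizes rest on assumed rates, correlations and slopes.

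**What to change.** In the Analysis subsection, replace the t-tests for HbA1c and weight with one mixed model for repeated measures per outcome:
- use all scheduled values, including weight at 6 and 18 months;
- fit categorical visit, arm-by-visit and baseline-by-visit terms, with unstructured covariance;
- analyse all patients as randomised, including HbA1c and weight still recorded in routine care after withdrawal, where consent allows;
- take the contrasts at the time points listed under Outcomes from this model, including 6 and 12 months post intervention, where data depend on fresh consent at month 24 and selection needs particular attention;
- keep t-tests as description only;
- add one sensitivity analysis for loss that is not at random, for example worsening the imputed values of AMOS drop-outs.

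Patients with only a baseline value carry no information on the contrasts in this model, so report their number by arm.

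The cost is a change of wording and slightly more analysis work. No new visits or patients are needed, and Stata and SPSS, both already named, can fit the model. It relies on loss being explained by observed values, a weaker assumption than the completer t-test needs.
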